## Introduction

Gastric cancer (GC) is the fifth most common cancer[1], with more than 900,000 new cases every year, and the third leading cause of cancer-related death worldwide[2].

Surgery and adjuvant treatment are the main treatment modalities for GC. Postoperative morbidity rates after gastrectomy vary across different studies, but total morbidity is more than 20–30% in most studies[3–8]. In a previous study by our group, morbidity was present in 31% of 1066 gastrectomies [9].

Data on postoperative morbidity predictors are heterogeneous. Patient (age, comorbidity, body mass index, serum albumin), tumor (local invasion and location), and surgery (open approach, total gastrectomy, lymph node dissection, and multi-organ resection) variables are described as potential factors for higher morbidity[3–5,8].

In our previous study, we did not have data on complication severity because this type of score did not exist at the beginning of that study[9]. In the past decade, complication severity has gained great importance, and use of the Clavien-Dindo classification has been widely adopted[10]. However, only a few studies have evaluated postoperative morbidity predictors according to complication severity for gastrectomy[6,7].

The aim of this study to identify predictors of severe postoperative morbidity after gastrectomy for gastric cancer (GC) and esophagogastric junction (EGJ) cancer and to evaluate long-term survival according to complications.

## Material and methods

This is a retrospective cohort study. We collect patients' demographics, tumor and surgery characteristics, and postoperative morbidity. All consecutive patients treated with a gastrectomy for GC or EGJ cancer are included. Only patients with stomach or EGJ adenocarcinoma are selected, and patients with other histology are excluded.

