### *Operative procedure*

Epidural analgesia is routinely employed in open surgery. Depending on the tumor's location, a total or subtotal gastrectomy is indicated. Surgery includes omentectomy with bursectomy and D2 lymph node dissection, according to the Japanese classifications in patients with curative gastrectomy[11]. Multi-organ resection, including spleen, pancreas, colon, and liver, is performed in cases of direct tumor invasion. Partial distal esophagectomy with a transhiatal approach and mediastinal anastomosis is employed for Siewert types II and III cancers, with frozen section intraoperative biopsy to confirm an R0 resection. Partial distal esophagectomy is considered a multi-organ resection when more than 2 cm of the esophagus was resected. Routine cholecystectomy is performed in curative cases and was not considered a multi-organ resection. A reconstruction, using Roux-en-Y, is performed after a total gastrectomy; Roux-en-Y or Billroth II is used for subtotal gastrectomy. Esophagojejunal anastomosis is performed with a circular stapler and a second layer of running monofilament suture. One or two prophylactic drains are used routinely[9]. A laparoscopic approach is employed in patients with clinical early GC who are not candidates for endoscopic resection and patients with advanced GC without clinical invasion of adjacent structures and with lymph node metastases only in the perigastric area[12].

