### *Postoperative management*

Patients start early respiratory and physical therapy the day following surgery. An oral contrast study is performed on postoperative day 5–7 for total gastrectomy; after this study, the patient starts an oral diet and prophylactic drains are removed.

Esophagogastric junction (EGJ) cancer is classified according to Siewert classification[13]. In this study, only EGJ cancer Siewert types II and III are included. Patients are staged using *TNM Classification of Malignant Tumors*, seventh edition[14].

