### *Statistical analysis*

Continuous variables are described by means and standard deviations or medians and interquartile range. Categorical variables are described with frequencies and percentage.

The following factors are analyzed: age, sex, comorbidity, American Society of Anesthesiologists (ASA) physical status, tobacco and alcohol consumption, body mass index (BMI), hematocrit, serum albumin level, tumor location, the use of preoperative chemotherapy, laparoscopic or open surgery, total or subtotal gastrectomy, duodenal stump closure, multi-organ resection, lymphadenectomy, reconstruction method, T status, lymph node metastasis, and resection margin. The T stage was grouped by T1–T2 and T3–T4 for analysis. Univariate and multivariate analyses are performed to identify predictors of severe postoperative morbidity; and predictors of long-term survival. All variables associated with severe morbidity with  $p < .05$  in the univariate analysis are subsequently entered into a Cox multivariate regression model with backward elimination. Significance is set at two-sided  $p < .05$ . All analyses are performed using the statistical SPSS IBM Statistics software program, version 22.

The local ethics committee approved this study. Informed consent of patients is waived because of the retrospective nature of the study. The study was designed in line with the PROCESS criteria[15].

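### The survival analyses leave out M status and curative intent, although the cohort appears to include non-curative gastrectomies

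*Combined protocol and SAP*

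**What the plan says.** Eligibility is open with respect to intent. Under Material and methods, "All consecutive patients treated with a gastrectomy for GC or EGJ cancer are included". The selection rules found are histology ("Only patients with stomach or EGJ adenocarcinoma are selected, and patients with other histology are excluded") and, under Postoperative management, restriction of junctional tumours to Siewert types II and III. Nothing excludes metastatic disease or resections without curative intent.

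The Operative procedure section twice singles out curative operations. It describes "D2 lymph node dissection, according to the Japanese classifications in patients with curative gastrectomy", and it says that "Routine cholecystectomy is performed in curative cases".

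The tumour and extent-of-surgery variables at the end of the factor list under Statistical analysis are "lymphadenectomy, reconstruction method, T status, lymph node metastasis, and resection margin". M status, overall stage and intent are absent. Yet the Postoperative management section says "Patients are staged using" the seventh edition of TNM, so an M category should exist for each patient.

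One aim in the Introduction is "to evaluate long-term survival according to complications". Five-year survival is the secondary outcome, and the Statistical analysis section also seeks predictors of long-term survival. The only stated rule for entering a multivariate model is a univariate p below .05 against severe morbidity, followed by backward elimination. No restriction, stratification or sensitivity analysis by intent or M status is planned.

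**The concern.** Patients resected with metastatic disease or without curative intent are expected to have much shorter survival than the rest, whatever happens after surgery. Two survival results could be affected, in different ways.

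- **Lymphadenectomy.** It is a listed factor, and the plan describes D2 for curative cases. A lesser dissection therefore partly marks non-curative surgery. If intent is not in the model, part of its effect on survival is credited to the dissection.
- **Severe complications.** Here confounding needs a second link: intent or M status must also be related to severe morbidity. If it is, the survival contrast by complication status carries part of the effect of intent. If it is not, there is no bias from this source.

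The entry rule makes this harder to escape. A variable that strongly predicts death but only weakly predicts morbidity can fail the screen or be eliminated, so even the partial proxies on the list are not assured of a place in the survival model.

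**Working it through.** **The plan's own figure.** The plan gives no figure on this point. Its only relevant number is the sample size of 116, which concerns morbidity. With 10.8% in the unexposed and OR 4.28, the exposed risk is 4.28 × 0.108 / (0.892 + 4.28 × 0.108) = 0.462 / 1.354 = 34.1%. A two-sided 0.05 test with 80% power, 1:1 groups (assumed, since no ratio is stated) and a continuity correction needs 58 per group, 116 in total. The figure reproduces, and the point does not depend on it.

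**Assumptions, none from the documents.** Non-curative share q = 2–20%. Five-year survival 55% in curative and 5% in non-curative cases, exponential. No true effect of D2 or complications, and no other covariates. D2 in 90% of curative and 20–50% of non-curative cases. Severe morbidity 10–15% in curative cases, and 0.7, 1, 1.5 or 2 times that in non-curative cases.

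**Hazards.** Monthly hazards are −ln(0.55)/60 = 0.00996 and −ln(0.05)/60 = 0.04993, a ratio of about 5.0.

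**One cell by hand** (q = 10%, D2 in 90% and 20%):

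- D2 group: 0.90 × 0.90 = 0.81 curative and 0.10 × 0.20 = 0.02 non-curative, so 0.02/0.83 = 2.4% are non-curative. Five-year survival is 0.976 × 0.55 + 0.024 × 0.05 = 53.8%.
- Lesser dissection: 0.90 × 0.10 = 0.09 and 0.10 × 0.80 = 0.08, so 0.08/0.17 = 47.1% are non-curative. Five-year survival is 0.529 × 0.55 + 0.471 × 0.05 = 31.5%.
- The ratio of log survivals is ln(0.538)/ln(0.315) = 0.54. The Mantel-Haenszel hazard ratio over 60 monthly intervals is 0.50. The true value is 1.00.

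**All cells, Mantel-Haenszel hazard ratio without adjustment for intent (approximate):**

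| Non-curative share | D2 vs lesser | Complications, ratio 0.7 | ratio 1.0 | ratios 1.5–2 |
|---|---|---|---|---|
| 2% | 0.80–0.88 | 0.99 | 1.00 | 1.02–1.04 |
| 5% | 0.64–0.75 | 0.97 | 1.00 | 1.04–1.09 |
| 10% | 0.50–0.63 | 0.95 | 1.00 | 1.08–1.17 |
| 20% | 0.40–0.53 | 0.91–0.92 | 1.00 | 1.13–1.27 |

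**Effect of a listed proxy.** Suppose positive margins in 60–80% of non-curative and 5% of curative cases (assumed), with a 10–20% non-curative share. Stratifying on margin alone moves the D2 hazard ratio from 0.40–0.63 to about 0.49–0.74. At ratios of 1.5–2 and 12% baseline morbidity, the complication hazard ratio moves from 1.08–1.26 to about 1.05–1.17. Bias is reduced but not removed.

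**The case against.** The strongest reply has four parts.

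1. **The non-curative share is inferred.** The documents never mention palliative gastrectomy or give a number of M1 patients. A reader might infer that the plan openly pools curative and palliative surgery. It does not say so; the qualifiers in the Operative procedure section only imply it. This stands, and it is why the range starts at 2%.
2. **Confounding of the complication comparison is not shown.** A reader might infer that it is certain, or that it must exaggerate the harm of complications. Neither follows. The documents do not relate intent to severe morbidity, and the direction could reverse: the Introduction names lymph node dissection as a possible risk factor for morbidity, and D2 is described for curative cases. The bias may also be small against sampling error. With 116 patients, 55% deaths (about 64) and 12–20% severe morbidity, all but the first assumed, the standard error of the log hazard ratio is 1/√(64 × p × (1 − p)), about 0.38 to 0.31. The logs of 1.02 and 1.27 are 0.02 and 0.24. This stands, although the standard error would shrink in a larger consecutive cohort and the bias would not.
3. **T, N and margin are listed and act as partial proxies.** This is true, so the unadjusted figures are near the upper end. But a patient with M1 disease can have clear margins and any T or N category, T is collapsed to two groups, and the entry rule does not guarantee that any of the three stays in the survival model.
4. **The plan seeks predictors and states no causal hypothesis about D2.** This is fair, and it rules out saying that a lesser dissection will look harmful solely because of intent. Lymphadenectomy is still a listed candidate, and an association produced by an omitted variable would be easy to misread.

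**Conclusion.** The point holds for the secondary survival analyses. Followed as written, the plan leaves out M status and intent, a major expected determinant of survival, although TNM staging should supply the M category.

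The lymphadenectomy–survival association is confounded by intent to the extent that non-curative cases are present, because the described practice ties D2 to curative surgery. Under the stated assumptions the spurious hazard ratio is about 0.40 to 0.88. The complication–survival comparison is affected only conditionally: 1.00 with no link between intent and severe morbidity, 0.91–0.99 at a ratio of 0.7, and about 1.02–1.27 at ratios of 1.5–2. All of these ignore other covariates, and adjustment for T, N and margin would bring them closer to 1.

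A reader might go further and conclude that the primary morbidity analysis is invalid or that its cohort must be restricted. The documents do not support that: the argument rests on survival, and keeping every consecutive patient suits the morbidity question. The change should be made because it is cheap and the omission is plain from the factor list.

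**What to change.** In the Statistical analysis section:

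- Add M status, taken from the TNM staging already planned, with R status where it is recorded. M status is safer than a retrospective judgement of whether an R0 resection was planned, which the documents do not say was recorded.
- State that M status stays in the survival model whatever the morbidity-based univariate screen and backward elimination would do, either forced in as a covariate or used as a stratification factor. Adding it to the candidate list alone is not enough, since the screen could drop it.
- Report the complication–survival comparison in M0 patients, and alongside it the whole cohort stratified by M status.
- Report the numbers of M1 and non-curative resections. If there are none, saying so closes the point.

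The primary morbidity cohort, the primary outcome and the stated sample size of 116 are unchanged. The cost is one variable drawn from staging records and one stratified analysis. The downside is fewer deaths, and so a less precise estimate, in the M0 analysis.

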### *Preoperative assessment*

The preoperative assessment is an upper gastrointestinal endoscopy, biopsy, complete blood count, liver function tests, electrocardiogram, and nutritional evaluation. Preoperative imaging is a thorax-abdomen-pelvis computed tomography (CT) scan.

### *Operative procedure*

Epidural analgesia is routinely employed in open surgery. Depending on the tumor's location, a total or subtotal gastrectomy is indicated. Surgery includes omentectomy with bursectomy and D2 lymph node dissection, according to the Japanese classifications in patients with curative gastrectomy[11]. Multi-organ resection, including spleen, pancreas, colon, and liver, is performed in cases of direct tumor invasion. Partial distal esophagectomy with a transhiatal approach and mediastinal anastomosis is employed for Siewert types II and III cancers, with frozen section intraoperative biopsy to confirm an R0 resection. Partial distal esophagectomy is considered a multi-organ resection when more than 2 cm of the esophagus was resected. Routine cholecystectomy is performed in curative cases and was not considered a multi-organ resection. A reconstruction, using Roux-en-Y, is performed after a total gastrectomy; Roux-en-Y or Billroth II is used for subtotal gastrectomy. Esophagojejunal anastomosis is performed with a circular stapler and a second layer of running monofilament suture. One or two prophylactic drains are used routinely[9]. A laparoscopic approach is employed in patients with clinical early GC who are not candidates for endoscopic resection and patients with advanced GC without clinical invasion of adjacent structures and with lymph node metastases only in the perigastric area[12].

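### Reconstruction method is screened separately from extent of resection although Billroth II can occur only after subtotal gastrectomy, so the univariate contrast is confounded and the screen can hide a real difference

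*Combined protocol and SAP*

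**What the plan says.** All places are in the combined protocol and SAP.

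- Operative procedure ties reconstruction to extent: "A reconstruction, using Roux-en-Y, is performed after a total gastrectomy; Roux-en-Y or Billroth II is used for subtotal gastrectomy". Extent in turn follows the site of the tumor: "Depending on the tumor's location, a total or subtotal gastrectomy is indicated".
- Material and methods pools both operations in one cohort: "All consecutive patients treated with a gastrectomy for GC or EGJ cancer are included".
- Statistical analysis lists the surgical and pathological candidates as "total or subtotal gastrectomy, duodenal stump closure, multi-organ resection, lymphadenectomy, reconstruction method, T status, lymph node metastasis, and resection margin". Extent and reconstruction are separate entries.
- The selection rule in the same section begins "All variables associated with severe morbidity with" and sets a univariate p<.05 threshold. Variables that pass go into a multivariate model with backward elimination. No factor is forced in.
- The Introduction names total gastrectomy among the suspected causes of morbidity: "surgery (open approach, total gastrectomy, lymph node dissection, and multi-organ resection) variables are described as potential factors for higher morbidity". It gives no effect size, and reconstruction is not on that list.

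Nothing restricts the reconstruction comparison to subtotal cases, stratifies it, or combines it with extent. Testing in the whole cohort is inferred from that silence, because the plan gives no coding for the variable.

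**The concern.** Surgical policy leaves one of the four extent-by-reconstruction cells empty: there is no total gastrectomy with Billroth II. A whole-cohort comparison therefore sets a mixture of total and subtotal patients (Roux-en-Y) against subtotal patients only (Billroth II). Whatever extent does to severe morbidity appears in the crude reconstruction result. Tumor location also differs between the groups, since it decides extent. Leak detection may differ too, because a contrast study is scheduled by extent: "An oral contrast study is performed on postoperative day 5–7 for total gastrectomy".

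Two errors can follow. With no reconstruction effect, the univariate result can make Roux-en-Y look harmful. With a real disadvantage of Billroth II after subtotal gastrectomy, the total gastrectomies can raise the Roux-en-Y risk enough to cancel it. The factor then fails the screen and later adjustment never sees it. Identifying predictors is the study's stated aim, so either error bears on what it reports.

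**Working it through.** **The plan's own figure.** Sample size gives 10.8% unexposed risk, OR 4.28, alpha 0.05, 80% power and 116 patients. Exposed odds = 4.28 × 0.108/0.892 = 0.518, so exposed risk = 0.518/1.518 = 34.1%. The two-proportion formula, two-sided, 1:1, with continuity correction, gives 58 per group, or 116. Without the correction it gives 50 per group, or 100. The figure reproduces and is not affected by this point.

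**Assumed inputs.** The documents give no case mix and no morbidity by extent. I assume 60% total gastrectomy and half of subtotals Roux-en-Y, so the cell shares are 0.6 total, 0.2 subtotal Roux-en-Y and 0.2 subtotal Billroth II. That is 300/100/100 at n=500 and 69.6/23.2/23.2 at 116. Only 116 is stated in the plan; 500 is an assumption.

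**Crude odds ratio with no reconstruction effect.** Roux-en-Y risk = (0.6 × total risk + 0.2 × subtotal risk)/0.8; Billroth II risk = subtotal risk.

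- 16% v 10%: (0.096 + 0.020)/0.8 = 14.5%; OR = (0.145/0.855)/(0.10/0.90) = 1.53
- 18% v 8%: (0.108 + 0.016)/0.8 = 15.5%; OR = (0.155/0.845)/(0.08/0.92) = 2.11
- 20% v 10%: (0.120 + 0.020)/0.8 = 17.5%; OR = (0.175/0.825)/(0.10/0.90) = 1.91

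**How often this matters.** I simulated 10,000 studies per scenario: uncorrected chi-square screen at two-sided .05, then a two-factor logistic model with likelihood-ratio backward elimination. Logistic regression was used because the outcome is binary; the plan's naming of a Cox model is a separate matter.

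| Total v subtotal risk | False screen pass, n=500 | n=116 | False retention in final model, n=500 | n=116 |
|---|---|---|---|---|
| 16% v 10% | 19% | 5% | 8% | 4% |
| 18% v 8% | 50% | 10% | 6% | 5% |
| 20% v 10% | 45% | 10% | 7% | 6% |

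Tested within subtotals, the false-positive rate is about 5% at n=500 and about 4% at 116. At n=500, roughly nine in ten or more of the false retentions leave reconstruction in the model without extent.

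**Sensitivity.** Take subtotal risk 10.8%, 40–70% total and 30–80% Roux-en-Y among subtotals. The null crude OR is 1.43–1.88 if the extent OR is 2, 1.81–2.73 if it is 3, and 2.25–3.79 if it is 4.28. It is 1.0 only if extent has no effect. With 50% total and 30% Roux-en-Y among subtotals, false final retention was 4–11% over n = 116, 300 and 1000 and these three extent ORs (1,000 runs each).

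**Masking.** Assume total 18%, subtotal Roux-en-Y 6% and Billroth II 14%. Within subtotals the Billroth II v Roux-en-Y OR is (0.14/0.86)/(0.06/0.94) = 2.55. In the whole cohort, Roux-en-Y risk = (0.108 + 0.012)/0.8 = 15.0% against 14%, so the contrast almost vanishes. At n=500 the whole-cohort screen detects a difference in about 5% of studies, and reconstruction reaches the final model in about 2%. The within-subtotal test detects it in about 47–49% across repeat runs. At 116 the within-subtotal test detects it in about 13–14%.

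**The case against.** The strongest reply is that the plan does not stop at the screen. Extent is itself a candidate, and when both factors enter, the empty cell means that reconstruction is estimated from subtotal patients alone. A model with an indicator for total gastrectomy and one for Billroth II is the same model as the proposed three-level factor. The larger the extent effect, the more reliably extent enters and displaces reconstruction. This stands. A reader might infer from the 19–50% screen rates that the study is likely to end by naming Roux-en-Y an independent predictor; final retention of about 4–8%, against a nominal 5%, does not support that.

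The second reply concerns the inputs. The case mix, the morbidity rates and n=500 are not in the documents, and at 116 false screen passage is only 5–10%. This also stands, and it is why both sizes are shown. The masking example was set close to full cancellation. Moving total-gastrectomy risk between 12% and 22% raises whole-cohort detection to at most about 18%, still well under the roughly 47% within subtotals. At 22% the pooled Roux-en-Y risk is (0.132 + 0.012)/0.8 = 18% against 14%, so the crude difference points the wrong way.

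A reader might also suppose that the point is weighty because reconstruction is a genuine choice by the surgeon. The documents do not say how Roux-en-Y or Billroth II is chosen after subtotal gastrectomy, so that argument is not used here.

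The reply does not reach two things: the confounded univariate result, and a variable that fails the screen and so never meets the adjustment.

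**Conclusion.** The point holds for the univariate result and for the p<.05 screen. Given the surgical policy and the missing restriction, the crude Roux-en-Y v Billroth II contrast is confounded whenever extent affects severe morbidity. The Introduction treats that as likely but does not quantify it. The bias is a null crude OR of about 1.5–2.1 under the main assumptions, and wider under the sensitivity ranges. The risk of a wrong final model from false retention is small. The risk of missing a real difference is larger in relative terms, but at 116 patients even the correct comparison has little power. Severity is moderate: one of about 20 candidates is affected, and neither the primary outcome definition nor the sample size depends on it.

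**What to change.** In Statistical analysis, replace the two entries with one three-level factor: total gastrectomy with Roux-en-Y; subtotal with Roux-en-Y (reference); subtotal with Billroth II. Screen, enter and remove it as a block. State that the Roux-en-Y v Billroth II contrast, univariate and multivariate, is reported within subtotal gastrectomy only, with its confidence interval.

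The cost is a recode of data already collected and a sentence or two of text. The factor uses the same two degrees of freedom as the two entries it replaces, and no information is lost, because total gastrectomies say nothing about Roux-en-Y against Billroth II.

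The downside is imprecision, which the report should state. With 116 patients, 40–70% total gastrectomy leaves about 35–70 subtotal cases. With 30–80% of these Roux-en-Y, power for the plan's own OR of 4.28 is about 16–65% (48% at the 60%/half mix).
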